**4. What is your plan for primary variable analysis?**

1. To evaluate the patient experience during a screening CESM to better understand if women find the experience of contrast injection to be too invasive or unpleasant to repeat or recommend to a friend.

**Data summarization:** Pre and post CESM survey responses that are binary or Likert scaled responses will be summarized by frequencies and percentages. Pre and post CESM survey responses that are continuous scaled responses will be summarized by the mean and standard deviation, the median and interquartile range, and the range of distribution.

**Statistical analyses:** Pre CESM procedure survey information will be utilized to predict: (a) if patients who undergo CESM are willing to have repeat CESM, and (b) if patients who undergo CESM would recommend CESM to a friend. Multivariate logistic regression will be used to predict these two outcomes. In the former case (a), the outcome variable will indicate if the patient was willing to have a repeat CESM, and in the latter case (b), the outcome variable will indicate if the patient would recommend CESM to a friend. The multivariate logistic regression model predictor variables will include age, level of education, and breast cancer related risk factor variables. Type III Wald tests will be conducted to determine which predictor variables are uniquely associated with outcome. A  $p \leq 0.05$  null hypothesis rejection rule will be used as the bases for identifying unique partial associations.

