**3. Provide a justification for the sample size used in this protocol.**

We have funding for 210 screening CESM subjects. This should allow us to evaluate for general attitudes toward CESM as well as some sub-analyses related to factors such as age, and family history. More specifically, we should be able to estimate the percentage of women who have a positive attitude toward CESM within  $\pm 3.5$  percentage units. This includes the worst case scenario in which the percentage is 50%, which is the scenario in which a binomial outcome variance is maximized.

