- All patients will undergo written consent for study participation after discussion of potential risks and benefits.

- Subjects who agree to participate in the CESM part of the study will complete a short survey regarding their interest and concerns about CESM PRIOR to the examination (Pre CESM Survey).
- The patient will then undergo CESM study which will serve as her annual breast imaging screening in place of annual screening mammogram.
- Since this is a screening exam, the study will not be interpreted immediately by the radiologist.
- Following the exam, the patient will be given a short survey (Post CESM Survey) that evaluates her experience during the CESM examination.

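### If few women are unwilling, a Wald-only rule can miss a predictor level that contains no unwilling women; a penalised likelihood-ratio test avoids this at almost no cost

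*Protocol*

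**What the plan says.** Protocol, Statistical Considerations, item 4 (primary variable analysis) defines two binary outcomes. For the first, "the outcome variable will indicate if the patient was willing to have a repeat CESM"; for the second, "the outcome variable will indicate if the patient would recommend CESM to a friend". The model is stated as follows: "Multivariate logistic regression will be used to predict these two outcomes". On its terms: "The multivariate logistic regression model predictor variables will include age, level of education, and breast cancer related risk factor variables". The number and coding of the risk factors are not given.

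The decision rule is: "Type III Wald tests will be conducted to determine which predictor variables are uniquely associated with outcome", with rejection at p≤0.05. No likelihood-ratio, exact or penalised test is named, and nothing is said about empty cells. Item 5.1 (secondary analysis) repeats the rule for willingness to undergo CESM.

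On who is surveyed, the Biomedical Research section says: "Subjects who agree to participate in the CESM part of the study will complete a short survey". On size, item 3 says: "We have funding for 210 screening CESM subjects". No expected percentage willing appears anywhere. The 50% in item 3 is only the worst case for precision.

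**The concern.** Both primary outcomes are asked of women who consented to a contrast examination and then had it. Women put off by an IV line or by contrast are largely outside the sample, so a small unwilling group is plausible.

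With few unwilling women, some level of education or of a risk factor may contain none. Ordinary maximum likelihood then has no finite estimate for that level. Its coefficient and standard error grow together, the standard error much faster, and the Wald statistic for that level goes to zero. A factor that clearly separates willing from unwilling women could be reported as having no unique association. Choosing another test after seeing this happen would be post hoc, so the choice belongs in the plan.

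**Working it through.** **Inputs.** From the Protocol: n=210, two binary outcomes, logistic regression, Wald tests, p≤0.05. Assumed: the unwilling rate, the predictor prevalences, the odds ratios and the covariate mix. The Protocol gives no power or effect size for these models, so there is no figure of its own to reproduce. Its ±3.5 points concerns a percentage, not these tests.

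**1. Binary predictor, empty level.** Take 0/42 unwilling against 21/168 (21/210 = 10%).
- Wald: when iteration stops, the coefficient is about −21 and its SE about 18,000. W = (21/18,000)² ≈ 0.0000014, so p>0.99.
- Ordinary likelihood ratio: 2 × [21 ln(21/168) + 147 ln(147/168) − 21 ln(21/210) − 189 ln(189/210)] = 2 × (−63.30 + 68.27) = 9.94, p=0.0016.
- Fisher exact: p=0.009.
- Firth coefficient (here the same as adding 0.5 to each cell): ln(0.5/42.5) − ln(21.5/147.5) = −2.52. Penalised likelihood-ratio p=0.008.

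**2. The same table with one or two unwilling women in the small level.**
- 1/42 against 20/168: ln(1/41) − ln(20/148) = −1.712; SE = √(1 + 1/41 + 1/20 + 1/148) = 1.040; z = −1.65, p=0.10.
- 2/42 against 19/168: −0.936/0.764 = −1.22, p=0.22.

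So, unadjusted, with 21 unwilling women and a 42-woman level, no split on the protective side reaches 0.05 by Wald.

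**3. Three-level predictor, 0/70, 3/70, 12/70.** In the limit the empty level adds nothing to the statistic but still uses a degree of freedom. What remains compares the other two levels: difference = ln(3/67) − ln(12/58) = −1.531; variance = 1/3 + 1/67 + 1/12 + 1/58 = 0.449; W = 2.343/0.449 = 5.22 on 2 df; p = exp(−5.22/2) = 0.074. Firth gives 0.0003.

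Other tables:

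| Unwilling/n | Wald p | Firth p |
|---|---|---|
| 0/52, 2/53, 4/53, 10/52 | 0.091 | 0.003 |
| 7/70, 8/70, 0/70 | 0.96 | 0.006 |

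**4. How often a 42-woman level is empty.** With no effect: 0.90^42 = 1.2% at 10% unwilling, 0.95^42 = 11.6% at 5%, and 0.80^42 < 0.01% at 20%. With 10% unwilling overall and an odds ratio of 1/3, the level's own rate is about 4.1% (0.8 × 0.115 + 0.2 × 0.041 = 0.10), so 0.959^42 ≈ 17%. With an odds ratio of 1/12 the rate is about 1.15%, so 0.9885^42 ≈ 62%.

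**5. Simulated power**, n=210, binary factor adjusted for other covariates. Odds ratios are for unwillingness. Where two sets of runs were made, the range is shown.

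| Prevalence | Unwilling | Odds ratio | Wald | Firth |
|---|---|---|---|---|
| 20% | 10% | 1/3 | 2.5–3% | 23–29% |
| 20% | 10% | 1/12 | 5% | 68–71% |
| 20% | 20% | 1/12 | 64% | 98% |
| 20% | 5% | 3 | 37.5% | 38% |
| 20% | 10% | 3 | 57% | 57% |
| 20% | 20% | 3 | 80% | 79% |
| 50% | 10% | 3 or 1/3 | 59% | 59–61% |

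Firth rejected in about 4–6% of null datasets.

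A level holding half the sample is emptied only by a very large effect. At a 15-fold odds ratio, Wald against ordinary likelihood-ratio power was 34% against 93% at 95% willing, 77% against 99% at 90%, and 98% against 100% at 80%. At 95% willing, Wald power fell from 38% to 34% as the odds ratio rose from 5 to 15, while likelihood-ratio power rose from 64% to 93%.

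**The case against.** **The ceiling is not documented.** A reader might infer that the outcomes will be near ceiling. The Protocol does not say so. Whether contrast injection is too unpleasant to repeat is the question under study, and consent precedes the injection. This stands: the point is conditional on the unwilling rate.

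**Not every empty level gives p near 1, and not every empty level marks a strong predictor.** Multi-level terms can give 0.07–0.09, as in step 3. With no true effect, a level of 15% prevalence was empty by chance in 21% of simulated trials at 95% willing. A nearly empty level can survive: 1/105 against 15/105 gives Wald p=0.006. This also stands. It limits how often a real association is lost, but does not rescue the test when a level is empty.

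**The consequence is bounded.** A reader might infer that the primary conclusion would be wrong. Item 4 also summarises the surveys by frequencies and percentages, and item 3 sets a precision target; neither uses Wald tests. The error is conservative, and a statistician would notice an SE in the thousands.

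**It may belong in the SAP.** A fallback for sparse data commonly does. Here, though, the Protocol itself fixes the test, so noticing the problem during analysis would force a departure from it.

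**The secondary model is different.** A reader might extend the fault to item 5.1. If that outcome were taken only among women who underwent CESM, it would be constant, which no test repairs. If women from the general survey are included, no ceiling is shown.

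**Conclusion.** The point holds conditionally for the two primary models. If about 10% or fewer of the 210 women (21 or fewer) are unwilling, the Wald rule can miss a clear association whenever a level is empty. It does so with p near 1 for a binary predictor, and possibly with p only modestly above 0.05 for a multi-level one. For a minority protective level the loss is large: power of about 3% against 23–29% at an odds ratio of 1/3, and 5% against 68–71% at 1/12. For such a level and an odds ratio of 1/12 it persists at 20% unwilling (64% against 98%). For a risk-raising level, or a moderate effect in a level holding half the sample, the tests agree.

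The unwilling rate, prevalences, effects and covariate mix are all assumptions. The inferential statements about predictors are at risk; the descriptive results are not. This is a worthwhile correction, not a flaw that invalidates the study.

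**What to change.** In Protocol, Statistical Considerations, item 4, replace the Type III Wald tests with Firth penalised-likelihood logistic regression, using penalised likelihood-ratio tests and profile-likelihood 95% confidence intervals for each predictor. Keep the same predictors and the p≤0.05 rule. The ordinary likelihood-ratio test is a weaker substitute: in sparse simulated data its null rejection rose to 9–10% for some terms, against at most about 6% for Firth. The same wording may be used in item 5.1 for consistency, without claiming the same problem there.

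The cost is one sentence and a standard software option, with no extra women or data. The downside is mild shrinkage of the odds ratios. The change does not make up for too few unwilling women: at 3% unwilling (about 6 women), Firth had only 25% power for a steep education gradient, against 4% for Wald. The change should be made before outcome data are seen.

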## 5. What is your plan for secondary variable analysis?

1. We will evaluate differences by age, education, and risk factors as to whether these drive willingness to undergo CESM.

**Data summarization:** Binary risk factors will be summarized by frequencies and percentages. Continuous scaled risk factors will be summarized by the mean and standard deviation, the median and interquartile range, and the range of distribution.

**Statistical analyses:** Multivariate logistic regression will be utilized to determine if there is an association between the willingness to undergo CESM and age, level of education, and breast cancer related risk factors. The outcome variable will be binary and the value 1 will be assigned if the patient is willing to undergo CESM and the value 0 will be assigned if the patient is unwilling to undergo CESM. Predictor variables will include age, level of education, and breast cancer related risk factors. Type III Wald tests will be conducted to determine which predictor variables are uniquely associated with outcome. A  $p \leq 0.05$  null hypothesis rejection rule will be used as the bases for identifying unique partial associations.

2. A secondary endpoint will evaluate differences in recall and PPV for biopsy recommendation compared to our practice norms for women with dense breasts during the same time interval.

**Data summarization:** Recall frequencies and positive predicted values (PPV) will be summarized in the traditional manner by frequencies and percentages for the former, and by percentages for the latter.

**Statistical analyses:** Recall frequencies and PPV for biopsy recommendation will be compared between the two study-groups by way of exact binomial methods.

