### 1. Provide the scientific background, rationale and relevance of this project.

Screening mammography reduces breast cancer mortality by 15-40%. However, the limitations of mammography have long been known regarding the ability to detect cancer in women with dense breast tissue. Interval cancers, presenting as a palpable or other clinical finding between screening intervals, are 5 times more likely in women with heterogeneously dense breast tissue and 17 times more likely in women with extremely dense tissue compared with women with predominately fatty breasts (1). This lack of an effective breast cancer screening modality has prompted breast density legislation- now in effect in 19 states. In 2011, Virginia became the 3rd state to have a breast density law enacted. However, more than 25 million women age 40-74 years have either heterogeneous or dense breast tissue on mammography (2). Any decisions regarding supplemental screening may be costly to our society.

[figure not shown]
The most common ancillary screening test performed after a mammogram is a screening ultrasound (US). Screening US detects about 30% more breast cancers than mammography alone (3-5). However, screening US is associated with a high false positive rate. Whereas women undergoing screening mammography have a 1-2% risk of undergoing biopsy, 5-7% of women undergoing screening US will be recommended to undergo biopsy. The positive predictive value (PPV) of biopsy recommendation for lesions identified at screening US is also quite low (7-9% cancers, versus 25-40% for mammography). The low specificity is the major downside of using US for ancillary screening of women with dense breast tissue. The cost associated with this examination is high- for every 100 exams performed, up to 7 biopsies will be performed, and up to 10 will have another US in 6 months due to an indeterminate lesion.

[figure not shown]
Contrast-enhanced spectral mammography (CESM) is an emerging modality that incorporates both anatomic (structural) and functional (enhancement) information of the breasts. CESM is an FDA approved imaging study for detection of breast cancer and is frequently used for diagnostic patients in the UVa Breast Care Center.

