### **Inclusion/Exclusion Criteria**

**1. List the criteria for inclusion for CESM**

- Female
- 40 to 69 years
- Previous normal mammogram (BI-RADS 1 or 2) showing heterogeneous or extremely dense breast tissue within last 24 months
- Scheduled for screening mammogram as part of the patient's clinical care

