**2. List the criteria for exclusion for CESM**

- No mammogram within last 24 months
- Fatty or scattered fibroglandular tissue on last mammogram
- History of allergy to iodinated contrast
- History of renal disease or renal function abnormalities
- Pregnant women
- History of diabetes

- History of paraproteinemia syndromes such as multiple myeloma
- History of collagen vascular disease
- History of vascular disease (coronary artery disease, myocardial infarction, carotid disease, peripheral vascular disease, or known visceral artery disease)
- Previously identified as high risk for breast cancer (>20% lifetime risk)
- Asthma
- Sickle Cell Anemia
- Currently on Dialysis
- If patient is age 60-69 years we will need to confirm that kidney function is normal. We will draw a small volume of blood and check this, unless patient has had a lab test showing normal kidney function in the last 30 days as part of standard of care.

**4. List any restrictions on use of other drugs or treatments.** none

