**2. What are the statistical considerations for the protocol?**

There are no specific statistical considerations. We are only planning to evaluate women's experience and willingness to undergo CESM in the screening setting. However, it should be noted that if modifications are made to the general survey questionnaire (IRB Submission #11378) after the first 50 patients have completed the questionnaire.

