**7. Will data from multiple sites be combined during analysis? No**

## Biomedical Research

**1. What will be done in this protocol?**

- Women age 40-69 years of age scheduled to undergo a screening mammogram at any one of our screening sites (Northridge, Orange, Zion Crossroads) or the UVa Breast Care Center will have their previous mammogram screened to see if there is evidence of heterogeneous or dense breast tissue (within 2 years). If so, the study nurse will contact the patient to see if they would like to participate in the CESM study. All patients having a CESM will have an appointment scheduled at the Breast Care Center, where CESM will be performed.
- In addition, study flyers approved by the IRB will be placed at UVa Imaging sites as well as primary care and gynecology offices.
- All women will have a urine pregnancy test at the Breast Care Center unless there has been no menstrual cycle for at least one year (postmenopausal) or history of hysterectomy.
- CESM is a mammogram performed after the injection of contrast via IV. Two images are taken almost simultaneously during the exam after the contrast is administered. The first image is essentially a standard mammogram. The 2nd image shows areas that take up the contrast (enhance) signifying increased blood flow. CESM studies are performed at the UVa Breast Care Center in the West Complex. Contrast administration is given following the same protocol of IV iodinated contrast administration as for CT scans elsewhere in the UVa Health System. Radiologists and technologists in the UVa Breast Care Center are trained in contrast administration and treatment of contrast reaction. Women having a CESM will have a 30 minute period post procedure to monitor for allergy to iodine contrast as per department SOP.
- Per department protocol, women age 60-69 will have serum creatine/GFR within 30 days or will have the test done prior to the CESM exam. If blood needs to be drawn prior to exam a BCC nurse or research nurse will draw 1 green top tube and send this to the Radiology Nursing area in main hospital. The blood will be processed for Creatinine and GFR on the I-STAT machine, results will be reported back to BCC. The standard mammogram portion of the CESM will be billed to the patients insurance as per standard of care. The administration of contrast and any cost related to the contrast enhanced portion of the CESM, will be paid for by the research study.

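### CESM recall is compared, with no adjustment named, with practice norms aligned on institution, density and calendar time but not on the trial's age, prior-mammogram and risk limits, so case mix could contribute to a difference

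*Protocol*

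**What the plan says.** Protocol, Statistical Considerations, question 5, item 2, plans to evaluate recall and PPV for biopsy recommendation "compared to our practice norms for women with dense breasts during the same time interval". The two quantities are to be "compared between the two study-groups by way of exact binomial methods". No covariate, matching, standardisation or further restriction is named for this comparison, and no significance level is attached to it. In item 1 of the same question, age and breast cancer risk factors are predictors in the regression for willingness to undergo CESM.

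Inclusion/Exclusion Criteria, question 1, limits trial women to ages 40-69 and requires a "Previous normal mammogram (BI-RADS 1 or 2) showing heterogeneous or extremely dense breast tissue within last 24 months". Question 2 excludes women without a mammogram in that window and women already identified as having more than 20% lifetime risk. It also lists several medical exclusions, such as diabetes, asthma, and renal or vascular disease.

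The study has no control group (Study Design: Biomedical, question 1) and no randomisation or stratification (Statistical Considerations, question 1). Statistical Considerations, question 2, gives the main purpose as women's "experience and willingness to undergo CESM in the screening setting".

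**The concern.** Recall may differ with a woman's age, with whether a recent normal examination is available, and with her risk. The trial selects on all three. As written, the norms are selected on none of them, so the planned comparison puts a more selected group beside a less selected one. An exact binomial comparison takes no covariates and cannot separate selection from modality.

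The Background and the Risk/Benefit Analysis criticise screening ultrasound for low specificity and present CESM as a possible alternative. A recall difference from practice norms could therefore be read as evidence about CESM, when part of it may come from who was eligible.

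**Working it through.** **Step 1: set the limits side by side.**

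| Feature | CESM women | Practice norms, as worded |
|---|---|---|
| Institution | UVa | UVa |
| Density | heterogeneous or extremely dense | dense |
| Calendar time | study period | same interval |
| Age | 40-69 | not stated |
| Prior mammogram | BI-RADS 1 or 2 within 24 months | not stated |
| Known lifetime risk above 20% | excluded | not stated |

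Three features are aligned and three are not.

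**Step 2: see what a mismatch could do.** The protocol gives no recall rate, norm value or power for this endpoint, so there is no figure to reproduce. Only n = 210 comes from the document. Everything else here is assumed:

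- b = recall in trial-eligible women: 8, 10 or 12%.
- s = share of norm women outside the trial's limits: 10, 20, 30 or 40%.
- r = recall in those women relative to eligible women: 0.8, 1.25, 1.5 or 2.0.
- CESM has no effect on recall; two-sided exact binomial test of 210 women against a fixed norm, rejecting at p ≤ 0.05.

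Norm recall = b × (1 − s + s × r). The apparent CESM difference is b minus this.

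Example: b = 10%, s = 0.4, r = 2.0 gives 10% × (0.6 + 0.8) = 14%, so CESM looks 4.0 points better. With r = 0.8 the norm is 10% × (0.6 + 0.32) = 9.2%, so CESM looks 0.8 points worse. At b = 12% the same two cells give 4.8 points better and 0.96 points worse, which are the extremes of the grid.

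False rejection rate at b = 10% (4.9% when there is no mismatch):

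| s | r = 0.8 | r = 1.25 | r = 1.5 | r = 2.0 |
|---|---|---|---|---|
| 0.1 | 4.9% | 3.8% | 4.7% | 6.8% |
| 0.2 | 5.7% | 4.7% | 6.8% | 10.1% |
| 0.3 | 5.7% | 4.7% | 6.5% | 21.4% |
| 0.4 | 7.6% | 6.8% | 10.1% | 37.6% |

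Over all 48 cells, the rate is at most 8.6% in 37 and above 10% in 11; those 11 all have r ≥ 1.5 and s ≥ 20%. It is above 20% in 5 cells, all with r = 2.0 and s ≥ 30%, with a maximum of 45.1%. With no mismatch it is 4.2-4.9%.

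**Step 3: compare with sampling error.** At 10% recall the 95% half-width for 210 women is 1.96 × √(0.1 × 0.9 / 210) = 4.06 points. In 11 of the 16 cells at b = 10% the shift is 1.0 point or less.

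**Step 4: cost of restricting the norms.** Half-width of the difference in points, at 10% recall with N norm women (N assumed): √(4.06² + (196 × √(0.09/N))²).

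- N = 5,000: 4.14. After removing 40% (N = 3,000): 4.20.
- N = 1,000: 4.46. After removing 40% (N = 600): 4.71.

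**The case against.** The best reply is that this treats silence as a choice. The comparator is named in one phrase, which does not say that women of every age, imaging history and risk level enter it. Restricting the norms later, for instance in a statistical analysis plan, would contradict nothing. That is true, and it makes the repair easy. But the protocol itself names both the comparator and the test, and the only limits it gives the comparator are density and time. Followed as worded, the groups are selected differently.

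The second reply is that this is a benchmark: no control group, no power, no decision attached, and a main purpose that concerns experience and willingness. This stands, and it limits the weight of the point.

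The third is that no material bias is shown. This also stands. All recall inputs are assumed, and three of the four ratios exceed 1, so the scenarios in which CESM looks better dominate by construction.

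Three stronger readings may tempt a reader, and the documents support none of them:

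- **That the comparison is biased in favour of CESM.** The protocol gives neither the recall of ineligible women nor their share of the norms, so no direction follows.
- **That the norms also fail to match on the screening indication.** Trial women must be "Scheduled for screening mammogram as part of the" patient's clinical care, but recall norms naturally mean screening norms.
- **That PPV is distorted by case mix as well.** Nothing in the document establishes this. The evident limit there is precision, a separate matter: the Background says that "women undergoing screening mammography have a 1-2% risk of undergoing biopsy", which in 210 women is 2.1 to 4.2 biopsies.

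**Conclusion.** The point holds as a possibility of bias in a secondary endpoint. The norms are aligned on institution, density and calendar time. They are not aligned on age, prior mammogram or known risk, and no adjustment is named, so a recall difference could partly reflect case mix.

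On the assumed grid the effect is usually small beside the sampling error. It becomes material only if a large share of norm women fall outside the trial's limits and their recall is clearly higher; the documents show neither. The main aim, patient experience and willingness, is unaffected. The change is worth making because it is cheap, not because material bias has been demonstrated.

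**What to change.** In Statistical Considerations, question 5, item 2, define the norm cohort as non-study women having standard screening mammography in the same interval who:

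- are aged 40-69;
- have heterogeneous or extremely dense tissue;
- have a BI-RADS 1 or 2 mammogram within the prior 24 months; and
- where this is recorded, are not known to be at high risk. The protocol does not show that lifetime risk is available for norm women, so this last filter must be conditional.

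Keep the exact binomial comparison. Add a sentence saying that the comparison is not causal, because two differences remain uncontrolled: volunteering (women are telephoned by the study nurse, and "study flyers approved by the IRB will be placed at UVa Imaging sites") and the medical exclusions. Standardising the norms to the age distribution of the CESM women may be added as an optional sensitivity analysis.

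The cost is a few lines of text, slightly more data extraction and a smaller comparator. On the assumed norm sizes, losing 40% of norm women widens the half-width of the recall difference by 0.06 points (4.20 − 4.14, from 5,000 women) or 0.25 points (4.71 − 4.46, from 1,000 women).
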